Patients with cardiogenic shock, regardless of the underlying etiology, present with hypotension, shortness of breath, altered mental status, signs of volume overload (elevated jugular venous pressure, pulmonary rales, lower extremity edema), and evidence of end-organ hypoperfusion. These patients are typically admitted to the Coronary Care Unit (CCU) for aggressive treatment to reverse the course of the disease. Standard of care therapy for these patients involves initiation of ionotropes and/or vasopressors along with diuretics. Often, mechanical circulatory support (i.e. Intra-arterial balloon pump or temporary left-ventricular assist devices) and invasive hemodynamic monitoring (i.e. placement of a pulmonary artery catheter) is necessary.

The results of the small trials mentioned above are encouraging, but larger randomized trials are necessary to establish the role of TH in patients with cardiogenic shock. We propose a first-ever randomized clinical trial to prospectively study the effects of TH in patients with cardiogenic shock. In addition to assessing the safety of TH in this patient population, hemodynamic parameters, echocardiographic assessment of cardiac function during hypothermia, as well electrocardiographic changes with hypothermia will be studied. The echocardiographic changes during TH have never been previously reported. Studying TH in patients with cardiogenic shock is important, as therapies for this highly morbid condition have remained largely unchanged for many years. Given the high mortality associated with cardiogenic shock despite advances in medical and mechanical support, the clinical implications of results from this trial may be large.

Objective

The purpose of the study is to prospectively randomize patients with cardiogenic shock to standard therapy plus therapeutic hypothermia or standard medical therapy alone in order to assess the safety of TH in patients with cardiogenic shock. This study will also help understand the physiologic effects of TH in cardiogenic shock. This will be a pilot study to establish the safety of TH and to assess tolerability of TH in this patient population.

Methods

A. Patient Population:

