5. TTE
6. Blood sample for future research

Endpoints

Primary safety endpoints:

1. Arrhythmia requiring medical therapy or therapy with temporary pacemaker
2. Bleeding requiring transfusions as a direct result of the cooling catheter insertion or secondary to resulting coagulopathy
3. Clinically important bloodstream infection, as confirmed with 2 positive blood cultures, or suspected sepsis in the absence of positive blood cultures with a sequential organ failure assessment (SOFA) score >2
4. Hypokalemia with potassium levels below 3.0mEq/L, not secondary to other identifiable causes

Secondary endpoints:

1. Hemodynamic changes during intervention period – Cardiac output/Cardiac Index, PCWP, SVR, mixed venous oxygen saturation (MVO₂), cardiac power index
2. Cumulative vasopressor and inotrope dose requirements (i.e. number of vasoactive and/or inotropic drugs used)
3. Echocardiographic % change in ejection fraction at 18-24 hours (from baseline)
4. In-hospital all-cause mortality

Procedures

Patients admitted to the Coronary Care unit (CCU) at the University of Chicago will be screened by the study investigators and the cardiology fellow on the CCU rotation. Patients meeting the inclusion criteria, as defined previously, will be identified and randomized after informed consent within 12 hours of presentation. Patients will be randomized to either TH plus standard medical care or to standard medical care alone. A pulmonary artery (PA) catheter will be placed at the bedside or in the Cardiac Cath lab if difficult anatomy is anticipated. As mentioned earlier, placement of a PA catheter is part of the standard of care for management of cardiogenic shock. Currently, patients who are admitted to the University of Chicago CCU with cardiogenic shock routinely undergo placement of PA catheter by the cardiology fellow in the CCU or in the cardiac cath lab. Data from the PA catheter is vital in initiating vasopressors/inotropes, assessing the response to the therapies, and possible need for escalation of therapy (i.e. mechanical support). In this study, patients in each arm will undergo PA catheter placement.

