Laboratory, echocardiographic, and hemodynamic parameters will be obtained for patients prior to randomization, near the end of 24 hour cooling therapy, and after 48-96 hours post-randomization. Core temperature will be measured via either thermal tip at the end of a transurethral urinary catheter or endotracheal temperature probe in intubated patients. Rewarming will be accomplished at 0.3°C per hour until temperature reaches 37°C.

Target Enrollment and Study Duration

In this initial pilot study, we anticipate enrolling 20 patients to the study, 10 randomized to standard medical therapy and 10 patients randomized to standard medical therapy and 24 hours of TH. We anticipate completing enrollment within 6 months.

Statistical Methods

The three-dichotomous primary endpoints will be analyzed using a two-sample independent proportion test or a Fisher's exact test with a Bonferroni method continuity correction for multiple endpoints. Furthermore, numerical secondary endpoints will be presented as either

mean \pm standard deviation or median (interquartile range) based upon the distribution of the data. In addition, all numerical secondary endpoints will be assessed using two independent t tests or Mann-Whitney U test for comparisons. Categorical variables will be tested with chi-square tests of association or Fisher's exact tests. Differences will be considered significant using an alpha value of 0.05 for a two-sided test. Analyses will be performed using STATA MP Version 14 (College Station, TX).

Potential risks and benefits to subjects

A. Benefits:

There is mounting evidence that TH has positive effects on cardiac function. Multiple studies have suggested that TH may offer particular benefit in cardiogenic shock. In this prospective trial, the patients will be randomized to TH or standard medical care using simple randomization. With TH, we expect increased cardiac output, increased contractility, lower SVR, and higher cardiac power index which will lead to improved hemodynamics and potentially decreasing pressor requirements.

B. Risks:

Anticipated adverse events that could possibly occur during the study include, but are not limited to:

1. *Risks associated with TH*
 - a. Shivering
 - b. Arrhythmia
 - c. Coagulopathy with or without clinically significant bleeding
 - d. Hyperglycemia
 - e. Hypothermia
 - f. Electrolyte abnormalities
 - g. Infections
2. *Risks associated with cooling catheter insertion*
 - a. Bleeding
 - b. Infection

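### The primary safety tests are not fixed: three endpoints are analysed but four are listed, two tests are allowed with no rule for choosing, and no interval supports the aim to establish safety

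*Combined protocol and SAP*

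**What the plan says.** **Number of endpoints.** The Endpoints section numbers four primary safety endpoints, each a yes/no outcome: arrhythmia needing treatment; "Bleeding requiring transfusions as a direct result of the cooling catheter insertion or secondary to resulting coagulopathy"; bloodstream infection or suspected sepsis; and "Hypokalemia with potassium levels below 3.0mEq/L, not secondary to other identifiable causes". Statistical Methods refers to three and names none of them.

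**Test and level.** Statistical Methods says "The three-dichotomous primary endpoints will be analyzed using a two-sample independent proportion test" and then offers Fisher's test as the alternative, in the words "exact test with a Bonferroni method continuity correction for multiple endpoints". It gives no rule for choosing, no divisor and no per-test level. Later in the same section comes the general statement "Differences will be considered significant using an alpha value of 0.05 for a two-sided test".

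**Aim.** The Objective uses two verbs. Patients are randomized "in order to assess the safety of TH in patients with cardiogenic shock", and then "This will be a pilot study to establish the safety of TH". Target Enrollment anticipates 20 patients, 10 per arm, and Patient Population specifies simple 1:1 randomization. Neither the protocol nor the DSMB charter plans a confidence interval or states an acceptable event rate.

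**The concern.** The primary analysis should be executable by someone who has only the plan. Here two statisticians could follow the text, choose different tests and levels, and reach different verdicts on the same counts. The trial is unblinded and the test is not fixed, so it could be chosen after the counts are known.

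The phrase about a Bonferroni continuity correction merges two unrelated procedures. Bonferroni divides the significance level among endpoints. A continuity correction adjusts a single test statistic for discreteness. The reader cannot tell whether the second was intended.

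The third gap concerns what the result can support. With 10 per arm, a non-significant comparison is likely even under substantial harm. If test verdicts are the only planned output for the primary endpoints, the report will not show how much harm the data leave open.

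**Working it through.** **Inputs from the documents.** 20 patients, 10 per arm; simple 1:1 randomization; two-sided 0.05; three endpoints (Statistical Methods) or four (Endpoints). The documents state no per-test level, power or sample-size derivation, so there is no figure of the plan's own to reproduce. They give no rates for these endpoints in this population, so every rate below is an assumption.

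**1. Level.**
- Three endpoints: 0.05/3 = 0.0167 per test.
- Four endpoints: 0.05/4 = 0.0125 per test.
- 0.0167 used on all four: 4 × 0.05/3 = 0.067, above 0.05.

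**2. Choice of test at 10 v 10.** With a and b events, pooled p = (a + b)/20 and z = |a/10 − b/10| / √[p(1 − p)(1/10 + 1/10)]. The continuity-corrected version subtracts 0.5 × (1/10 + 1/10) = 0.1 from the numerator.

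Worked example, 5 v 0: p = 0.25 and the standard error is √(0.25 × 0.75 × 0.2) = 0.1936.
- Uncorrected: z = 0.5/0.1936 = 2.58, p-value 0.0098.
- Corrected: z = 0.4/0.1936 = 2.07, p-value 0.0389.
- Fisher: 2 × C(10,5)/C(20,5) = 2 × 252/15,504 = 0.0325.

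All 121 tables were enumerated. These are the ones, apart from mirror images, on which the choice of test changes a verdict:

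| Events, TH v control | Uncorrected z | Fisher | Corrected z |
|---|---|---|---|
| 5 v 0, 10 v 5 | 0.0098 | 0.0325 | 0.0389 |
| 7 v 1, 9 v 3 | 0.0062 | 0.0198 | 0.0225 |
| 8 v 2 | 0.0073 | 0.0230 | 0.0253 |
| 6 v 0, 10 v 4 | 0.0034 | 0.0108 | 0.0147 |

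The first three rows are every table where uncorrected z and Fisher disagree, and they disagree at both 0.0125 and 0.0167. The last row is every table where corrected z and Fisher disagree, and only at 0.0125.

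Chance that uncorrected z and Fisher disagree on one endpoint (10 v 10, either level): 0.1% and 0.6% at equal assumed rates of 10% and 20%; 4.0%, 8.9%, 14.0% and 17.9% at an assumed 10% v 30%, 40%, 50% and 60%.

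**3. Divisor alone.** At 10 v 10 no Fisher or uncorrected z p-value lies between 0.0125 and 0.0167, so the divisor changes no verdict by either test. Simple randomization gives exactly 10:10 with probability C(20,10)/2^20 = 184,756/1,048,576 = 17.6%. At other splits the divisor can matter. For 6/11 v 0/9, Fisher gives [C(11,6) + C(9,6)]/C(20,6) = (462 + 84)/38,760 = 0.0141, which is significant at 0.0167 but not at 0.0125. Averaged over simple randomization, the divisor changes the Fisher verdict in 0.04% and 0.2% of trials at equal rates of 10% and 20%, and in 1.3%, 3.3%, 5.7% and 7.1% at 10% v 30%, 40%, 50% and 60%.

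**4. What a non-significant test leaves open.**
- 0/10 events: Clopper-Pearson upper 95% limit = 1 − 0.025^(1/10) = 30.8%.
- 4 v 0: Fisher p = 0.087, yet the difference is +40 points (Newcombe 95% interval 3.8 to 68.7).
- Power per endpoint at 0.0125, 10 v 10:

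| Assumed control v TH rate | Fisher | Uncorrected z |
|---|---|---|
| 10% v 30% | 1.7% | 5.7% |
| 10% v 40% | 6.3% | 15.2% |
| 10% v 50% | 15.5% | 29.5% |

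**The case against.** **The effect of test choice depends on how one phrase is read.** If three endpoints and the continuity correction are both taken literally (corrected z at 0.0167), the choice of test changes no 10 v 10 verdict. Averaged over simple randomization, the two tests then disagree in 1.7%, 4.3%, 7.5% and 9.6% of trials at an assumed 10% v 30%, 40%, 50% and 60%. A common rule, Fisher when an expected count is below 5, would also settle four of the five disputed tables (8v2 sits exactly at 5). This stands as a limit on size. It does not remove the ambiguity, because the plan states neither that rule nor which reading is meant.

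**Three may be a stale count.** The Endpoints section heads all four items as primary, so this is the natural reading. A reader might instead infer that the fourth endpoint falls under "Categorical variables will be tested with chi-square tests of association" at 0.05, giving a nominal family level of 3 × 0.0167 + 0.05 = 0.10. The documents do not support that: the sentence follows two on secondary endpoints and mentions no primary one.

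**This is a pilot, and no decision is tied to these p-values.** A reader might infer that a non-significant result will be declared proof of safety. The plan does not say so, and the Objective also says assess. DSMB review of individual adverse events does not depend on these tests. Intervals could also be worked out from reported counts. All this is fair, but the plan chose multiplicity-adjusted tests for its primary endpoints and set an aim that they cannot support alone.

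**Unequal ascertainment.** A reader might extend the point to bleeding, which is defined partly by the cooling catheter, and to hypokalemia, for which scheduled potassium checks differ by arm. That is a separate question and is not argued here.

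**Conclusion.** The point holds. The number of endpoints behind the Bonferroni level is inconsistent within the current text, and the primary test is left open. The choice of test is the larger issue: if the proportion test is uncorrected, it decides the verdict on five 10 v 10 tables and their mirrors, which are mostly tables that would suggest harm. If it is corrected, this shrinks to 6v0 and 10v4 and their mirrors, at 0.0125 only. The divisor is the smaller issue: it changes nothing at 10 v 10 by Fisher or uncorrected z, and matters only at unequal splits or under the corrected test.

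The lack of planned intervals bears most on the stated aim. With Fisher power of 6.3% for an assumed 10% v 40%, a non-significant test says little about safety. The tables, p-values and upper limit follow from 10 per arm alone. The power and disagreement percentages rest on assumed rates.

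This should be fixed before analysis. It does not call the conduct of the trial or its DSMB oversight into question.

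**What to change.** 1. Replace the first sentence of Statistical Methods with:

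> For each of the four dichotomous primary safety endpoints, the event rate in each arm will be reported with a Clopper-Pearson 95% interval and the risk difference (TH minus control) with a Newcombe 95% interval, not adjusted for multiplicity. Each endpoint will be compared by a two-sided Fisher's exact test at 0.05/4 = 0.0125 as a supportive analysis. A non-significant test will not be taken as evidence of safety.

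   This removes the proportion test and the reference to a continuity correction.

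2. If only three endpoints are meant to be primary, name in Endpoints the one that is not, and use 0.05/3 = 0.0167.

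3. In Objective, replace the aim of establishing safety with that of estimating the safety event rates.

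No special analysis rule for bleeding or hypokalemia is proposed. Separately, the sponsor should reconcile the potassium schedule: Mitigating Risks associated with TH gives every 4–6 hours, and Appendix 1 gives every 4 hours in cooled patients.

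**Cost.** Wording only, with no added patients or data. Fisher is less sensitive to harm than uncorrected z (6.3% v 15.2% power at an assumed 10% v 40%). The intervals are unadjusted: for four independent 95% intervals, the nominal chance that at least one misses is 1 − 0.95^4 = 18.5%. The stated aim also becomes more modest.

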INVESTIGATIONAL PLAN

Study Title: Cardiogenic SHock Intravascular CooLing TriaL (CHILL-SHOCK)

Principal Investigator: [name]

Co-Investigators:

- [name]
- [name]
- [name]
- [name]
- [name]
- [name]
- [name]
- [name]
- [name]
- [name]
- [name]
- [name] [name], PhD
- [name], APN
- [name]

Sponsor: Investigator initiated with support from ZOLL Circulation, Inc.

Intervention: Therapeutic hypothermia using FDA approved ZOLL Intravascular Temperature Management (IVTMTM) system to achieve core temperature of 32-34° for 24 hours in patients who present with cardiogenic shock.

Manufacturer of Intervention: ZOLL (Chelmsford, MA)

Background

Cardiogenic shock complicates 2-8% of all myocardial infarctions in hospitalized patients and despite advances in revascularization and mechanical support, the mortality rate in these patients can be as high as 50% during the index hospitalization.¹ Cardiogenic shock from alternative causes such as advanced heart failure, acute myopericarditis, stress-induced cardiomyopathy, and acute valvular regurgitation are also associated with significant morbidity and mortality.

Hypothermia, as defined by 32-34° Celsius, has been proposed as a potential adjunctive therapy in patients with cardiogenic shock. The role of mild hypothermia has been well established in out of hospital cardiac arrests due to ventricular tachycardia or ventricular fibrillation for improved neurological outcome.² In fact, the American Heart Association (AHA) guidelines recommend therapeutic hypothermia (Class I recommendation) with targeted temperature of 32°C to 34°C for 12 to 24 hours in patients who suffer out-of-hospital cardiac arrest due to ventricular fibrillation (VF).³ AHA also recommends induced hypothermia for patients after in hospital cardiac arrest due to any initial rhythm or after out-of-hospital cardiac arrest due to pulseless electric activity or asystole. This is a Class IIb recommendation, compared to Class I for out-of-hospital VF arrest.

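### The primary safety proportions have no stated window, denominator or rule for death before an event, so they cannot support a safety conclusion on their own

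*Combined protocol and SAP*

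**What the plan says.** The Objective is to randomize patients "in order to assess the safety of TH in patients with cardiogenic shock". Endpoints lists four primary safety endpoints:

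1. an arrhythmia that needs drug treatment or temporary pacing
2. transfused bleeding, worded as "Bleeding requiring transfusions as a direct result of the cooling catheter insertion or secondary to resulting coagulopathy"
3. infection of the bloodstream proven by culture, or culture-negative suspected sepsis that meets a SOFA condition
4. potassium below 3.0 mEq/L without another identifiable cause

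Death is in none of them. It appears as the fourth secondary endpoint, "In-hospital all-cause mortality".

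Statistical Methods then states "The three-dichotomous primary endpoints will be analyzed using a two-sample independent proportion test". It allows Fisher's exact test instead and mentions a Bonferroni adjustment. The count of three does not match the four listed; that is a separate error and should be corrected at the same time. The section does not say over what period an event counts, which patients form the denominator, or what happens to a patient who dies before an event. Mortality falls under the general rule of a chi-square or Fisher's exact test for categorical variables.

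The Data Safety Monitoring Board section collects adverse events during the index hospitalization, while Appendix 1 also schedules adverse events at 30 and 90 days. Neither is tied to the primary endpoints. Background says of shock complicating myocardial infarction that "the mortality rate in these patients can be as high as 50% during the index hospitalization". Target Enrollment gives 20 patients, 10 per arm.

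**The concern.** Death prevents a later arrhythmia, bleed, infection or low potassium, so it competes with every primary endpoint. In this population it may be common. A bare proportion then mixes two things: how often events occur, and how long patients live to have them. If one arm has more early deaths, its event proportions can fall for that reason alone.

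The pilot exists to describe safety, and at 10 per arm its message will rest on observed rates, where one patient is 10 points. Those rates could be read as reassuring when they partly reflect deaths, or the denominator could be settled after the data are seen.

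**Working it through.** The plan gives no event rate, effect size or power, so it has no figure of its own to reproduce. What follows is an illustration.

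**Inputs from the protocol.** In-hospital mortality up to 50% (Background; shock complicating infarction), used for control; 10 patients per arm.

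**Assumptions, not in the protocol.** Event risk in the absence of death, q, is 20% or 40% and equal in both arms. Mortality m in the hypothermia (TH) arm is 70% or 90%; the latter is extreme. Event and death hazards are constant and independent over one common window.

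**Formula.** Let a = −ln(1 − q) and d = −ln(1 − m). The proportion with an event before death, among all randomized, is

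a/(a + d) × [1 − exp(−(a + d))].

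**Example, q = 20%.**
- Control, m = 50%: a = 0.223, d = 0.693, sum 0.916. 0.223/0.916 × (1 − 0.40) = 14.6%.
- TH, m = 70%: d = 1.204, sum 1.427. 0.223/1.427 × (1 − 0.24) = 11.9%.

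| Mortality, control v TH | q | Observed events, control v TH | Apparent advantage of the deadlier arm |
|---|---|---|---|
| 50% v 70% | 20% | 14.6% v 11.9% | 2.7 points |
| 50% v 70% | 40% | 29.7% v 24.4% | 5.3 points |
| 50% v 90% | 20% | 14.6% v 8.1% | 6.5 points |
| 50% v 90% | 40% | 29.7% v 17.1% | 12.6 points |
| 30% v 50% | 20% | 16.9% v 14.6% | 2.3 points |
| 30% v 50% | 40% | 34.2% v 29.7% | 4.5 points |
| 10% v 20% (short window) | 20% | 19.0% v 18.0% | 1.0 point |

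**If every death comes before any event,** the observed proportion is (1 − m)q. At 50% v 70% this gives 10% v 6% (q = 20%) or 20% v 12% (q = 40%), a gap of 4 to 8 points.

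**Masking.** If TH raises the event hazard by 25% and mortality is 50% v 70%, the observed rates are 14.6% v 14.5% (control q = 20%) or 29.7% v 29.2% (control q = 40%). The excess disappears from the table.

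**The denominator matters.** In the worked example the three outcomes by arm are:

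| | Event | Death without event | Alive without event |
|---|---|---|---|
| Control | 14.6% | 45.4% | 40.0% |
| TH | 11.9% | 64.1% | 24.0% |

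Dropping those who died without an event gives 14.6/(14.6 + 40.0) = 26.8% v 11.9/(11.9 + 24.0) = 33.1%. The same patients now point the other way. Neither contrast alone describes safety; the three columns together do.

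**Composite.** Death or event is 1 − (1 − m)(1 − q): 1 − 0.5 × 0.8 = 60% v 1 − 0.3 × 0.8 = 76%. For q = 40% it is 70% v 82%.

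**Precision at 10 per arm.** The approximate 95% half-width for 60% v 76% is 1.96 × √(0.60 × 0.40/10 + 0.76 × 0.24/10) = 40 points, around a difference of 16. Fisher's test at 0.05 would detect these composites with probability 3.9% and 2.5%. For a single primary endpoint with no control events, 6 of 10 TH events are needed (p = 0.0108) at either 0.05/3 = 0.0167 or 0.05/4 = 0.0125. The risk is therefore a misleading description, not a false significant result.

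**The case against.** A reader might infer that the plan scores dead patients as safe and that this is an error in the primary analysis. The protocol does not say so. It names a test and leaves the denominator open; counting an early death as a non-event is only the default over all randomized patients. Nor is that default wrong in itself. With every patient followed to death or the end of the window, the crude proportion is the cumulative incidence with death as a competing event, a legitimate quantity when mortality is shown beside it.

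A reader might also infer that death is left out of the trial. It is not. In-hospital mortality is compared between arms, an adverse event that led to death is serious under Appendix 2, and the DSMB reviews the efficacy and safety endpoints after 4 and 10 subjects and at the end. With 20 patients, a large excess of deaths would be noticed.

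Nor do the documents show that the comparison will favour hypothermia. Appendix 1 schedules 4-hourly potassium checks only for cooled patients, and bleeding from cooling-catheter insertion can arise only in that arm; both push against hypothermia. A treated arrhythmia before death still counts. The mortality differences above are assumed, the 50% is an upper figure for one etiology among several admitted, and over a short window the effect is about 1 point.

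All of this stands, and it limits the claim. It does not supply the missing rule. Two separate totals, one for events and one for deaths, do not show how many patients died without an event, and DSMB review does not define how the primary result is calculated.

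**Conclusion.** The concern holds as a gap in the definition of the primary analysis: the window, the denominator and the handling of death before an event are unstated, for endpoints in which death is a foreseeable competing event. Neither open reading supports a stand-alone safety conclusion. Counting early deaths as non-events can lower the rates in an arm with more early deaths; dropping them selects patients on a post-randomization outcome.

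With equal underlying event risk, the distortion is about 1 point over a short window with deaths of 10% v 20%, and roughly 3 to 13 points over a hospital stay with 50% v 70% to 90% mortality. These sizes rest on assumed rates and independent constant hazards. The net direction across all sources of bias is uncertain. The separate mortality endpoint mitigates the problem but does not remove it.

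**What to change.** In Statistical Methods:

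1. Keep all randomized patients in the denominator of each primary endpoint, by assigned arm.
2. Use one common window for the primary endpoints and death. The index hospitalization is one candidate, since mortality and adverse event collection already use it.
3. Tabulate each primary endpoint by arm as event, death without event, and alive without event.
4. Add death or any of the four primary safety events, by arm with an exact confidence interval, as a descriptive supporting analysis.
5. State that no safety conclusion will be drawn from an individual endpoint without reading it with this table.
6. Correct the endpoint count to match Endpoints.

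**Cost.** Plan wording, a three-way layout for the endpoint table and one supporting analysis. The data are already collected, and no alpha is spent because the additions are descriptive. The drawback is that the composite gives equal weight to events of unequal importance and is very imprecise at 10 per arm, so it must not be presented as a powered test. The three-way table is the part that matters most.
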